1.2 Schema / Study Flow Diagram

Figure 1: MHAPPS Trial Flow Diagram

MHAPPS Trial Protocol

SLHS Applied Research

December 30,2020

2. Research Question & Specific Aims

Research Question: How can health systems support mental health among providers, employees, and patients during the COVID-19 era while minimizing the burden on the health system?

Specific Aims.

- **Aim 1:** Measure the prevalence of mental distress including loneliness, anxiety, depression, substance use, suicide ideation and other suicide-related risk factors in providers, staff, and patients served by SLHS. Describe differences associated with age, sex, race, ethnicity, urban or rural residence, living situation, occupation, local COVID-19 prevalence, perceived risk related to COVID-19, and masking and social distancing practices.
- **Aim 2:** Compare the effectiveness of two versions of the Caring Contacts intervention ((1) introductory phone or video call (phone call) followed by text messages (CC+), versus (2) text messages alone (CC)) to reduce loneliness and improve mental health outcomes among SLHS patients, providers, and staff experiencing mental distress during the COVID-19 era.
 - **Aim 2 Hypothesis:** We hypothesize that including an introductory phone call with the Caring Contacts intervention will yield better mental health outcomes among providers, staff, and patients experiencing mental distress than a Caring Contacts intervention with no introductory phone call.

3. Introduction

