13.1 General Analytic Approach

Aim 1: Descriptive statistics will be used to summarize cross sectional survey results as well as baseline demographic and other exposure variables. Linear regression models or generalized linear regression models GLM with robust standard errors will be used to assess the association between variables of interest.

Aim 2: The primary analysis will compare the effectiveness of the two interventions (CC+ and CC) delivered to two populations (patients and providers/staff), potential confounding, effect modification, and mediation will be handled through study design (e.g. use of randomization to assign individuals to interventions), and statistically through stratification (population). Other published studies related to Caring Contacts have shown that patient-centered outcomes such as suicidal ideation change over a 6-month period in response to receipt of these interventions.⁵¹

Analyses will be stratified for patients and providers/staff, modeling the effects of intervention separately in these population groups. There is very little evidence regarding the effect of Caring Contacts on healthcare workers, and we hypothesize that the magnitude of effect may differ by population group. Generating evidence of the effectiveness of Caring Contacts with and without an introductory phone call in healthcare workers is the primary goal of this heterogeneity of treatment effect (HTE) analysis. **Linear regression with robust standard errors will be used to determine whether the primary outcome differs between CC+ vs CC.**

Linear regression and GLM models will be used in the analysis of the secondary outcomes. Robust/sandwich standard errors will be used to allow for departures of the observed standard errors from classic model assumptions.

All data analyses will be completed using appropriate statistical software (such as R and R Studio, SPSS, Stata, SAS, Python, and/or Microsoft Excel). Statistical significance will be determined based on a type I error (alpha) of 0.05 (two-sided). Confidence intervals will be reported in addition to p-values.

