Variables will be measured through the Aim 1 survey or Aim 2 Baseline survey and reported using descriptive statistics. Potential effect modifiers will be assessed and include age, sex, gender identity, sexuality, race/ethnicity, religion, employment, urban/rural residence, drug/alcohol use, suicidal ideation at baseline, baseline depression score, baseline anxiety score, baseline stress score, baseline quality of life, measures of socioeconomic status and/or other variables related to the specified outcomes of interest. Data will be analyzed according to both an intention to treat protocol and per protocol received. Please see section 5.4 *Populations for Analyses* for further detail.

This study will report the distribution of key variables to facilitate assessment of the study's internal and external validity. At a minimum, this study will report the distribution of key variables within the analytic population (key variables are defined as those that are included in the causal diagram at the beginning of the *Research Design* section of this Research Plan). Missing data will be assessed on a regular basis through routine data reports. These reports will allow the investigators to assess the cause of missing or anomalous entries, and address these if possible. If missing values cannot be retrieved, the reason for the missingness will be recorded in data comments available through REDCap. Study staff will record the reason for any participant drop-out during the 6 months of follow-up.

[13.2 Power & Sample Size for Aim 2](#)

The total sample size for the aim 2 trial is 660 participants. For each stratum (patients, providers/staff), a sample of 330 subjects (165 in each arm) allows 80% power to detect a difference of 5 units in the primary outcome (loneliness) if a minimum of 70% of participants are retained through study completion.

[13.3 Duplicate Surveys](#)

A data cleaning step will be included to identify surveys completed twice by the same individual. This may occur, for example, when an individual is both a provider/staff person and a patient at SLHS. If duplicate surveys are identified, the first will be retained, and the second will be excluded from the research.

[13.4 Missing Data](#)

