5 ANALYSIS SETS/POPULATIONS/SUBGROUPS

We plan to survey up to 4,000 participants to address Aim 1. The total sample size for the Aim 2 trial is 660 participants, selected as a subset of those who complete the Aim 1 survey. For each stratum (patients, providers/staff), a sample of 330 participants (165 in each arm) allows 80% power to detect a difference of 5 units in the primary outcome (loneliness) if a minimum of 70% of participants are retained through study completion.

5.1 Inclusion & Exclusion Criteria: Aim 1

Provider & Employee Inclusion Criteria

- Provider or Employee at St. Luke's Health System
- Adults ≥ 18 years of age
- Proficient in spoken and written English language

Provider & Employee Exclusion Criteria

- Individuals who are unable or unwilling to provide informed consent to participate
- Individuals who are study staff for this study or the SPARC Trial
- Individuals who are participants in the SPARC Trial

Patient Inclusion Criteria

- Patient at a SLHS ED or primary care study site
- Current MyChart account user
- Adults ≥ 18 years of age
- Minors 12-17 years of age
- Proficient in spoken and written English language

Patient Exclusion Criteria

- Individuals who are unable or unwilling to provide informed consent to participate.
- Individuals who are participants in the SPARC Trial

5.2 Inclusion & Exclusion Criteria: Aim 2

Provider & Employee Inclusion Criteria

- Moderate or high score for loneliness, suicide ideation, psychological stress, anxiety, or depression:
 - NIH Toolkit Loneliness raw score of 13 or greater; or
 - C-SSRS score of 3 or greater; or
 - NIH Toolkit Perceived Stress raw score of 31 or greater for adults; or
 - GAD7 score of 11 or greater; or
 - PHQ9 score of 10 or greater
- Access to a phone for the duration of the study with the ability to receive text messages and phone calls

Provider & Employee Exclusion Criteria

- Individuals who are unable or unwilling to provide informed consent to participate
- Individuals who are study staff for this study or the SPARC Trial

Patient Inclusion Criteria

- Moderate or high score for loneliness, suicide ideation, psychological stress, anxiety, or depression:
 - NIH Toolkit Loneliness raw score of 13 or greater for adults and 16 or greater for adolescents; or

- C-SSRS score of 3 or greater; or
- NIH Toolkit Perceived Stress raw score of 31 or greater for adults or greater than 33 for adolescents; or
- GAD7 score of 11 or greater; or
- PHQ9 score of 10 or greater

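### The plan hypothesises that the effect may differ between patients and providers/staff but specifies no estimate of that difference; one secondary contrast would supply it at little cost

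*Protocol*

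**What the plan says.** Protocol 13.1 states that "we hypothesize that the magnitude of effect may differ by population group", describes the stratified work as a heterogeneity of treatment effect analysis, and relies on randomisation and on stratification by population to deal with effect modification. It then gives the aim of that analysis: "Generating evidence of the effectiveness of Caring Contacts with and without an introductory phone call in healthcare workers is the primary goal". It adds that "Confidence intervals will be reported in addition to p-values".

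The formal Aim 2 hypothesis in Protocol section 2 compares the two interventions only: "We hypothesize that including an introductory phone call with the Caring Contacts intervention will yield better mental health outcomes among providers, staff, and patients" who are in distress.

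The power statement in Protocol 13.2 is per stratum: "For each stratum (patients, providers/staff), a sample of 330 subjects (165 in each arm) allows 80% power to detect a difference of 5 units". SAP section 5 repeats it on the condition "if a minimum of 70% of participants are retained through study completion". SAP 7.2.1 and 7.2.2 fit every Aim 2 model separately in the two populations. Protocol 13.1 and SAP 6.5 say that potential effect modifiers will be assessed. Their lists include employment but not the patient/staff stratum, and no method is given.

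On the other subgroups, Protocol 13.5 and SAP 5.4 promise separate effect estimates and say that the study was not powered for them. SAP 7.2.3 lists the subgroups without saying which data will be used. SAP 7.3 draws missing 6-month outcomes from donors who share treatment arm, baseline loneliness tertile and study population.

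**The concern.** The quantity that addresses the hypothesis in Protocol 13.1 is the effect in patients minus the effect in providers/staff. No interaction term, contrast or statement of its precision appears in Protocol 13.1 to 13.5 or in SAP 5.4, 6.5 or 7.2.1 to 7.2.3. If the comparison is first made after the results are known, it is post hoc. Readers shown two separately tested strata will compare them anyway, and the plan gives them no agreed quantity for doing so.

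The second point is separate. A participant whose 6-month score is imputed under SAP 7.3 receives a donor's score regardless of subgroup. Any real difference in treatment effect between, say, urban and rural participants is diluted among the imputed records.

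**Working it through.** **Inputs.** Two-sided alpha 0.05 (Protocol 13.1); 165 per arm per stratum, 80% power, 5 units, at least 70% retained (Protocol 13.2, SAP 5). Neither document gives an SD. Equal SD and equal retention in the two strata are assumed.

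**Plan's own figure.** Without an SD, 165 cannot be reproduced independently, so the SD is back-solved. Evaluable per arm: 0.70 × 165 = 115.5. SE of a stratum effect: 5 / (1.960 + 0.842) = 1.785. Implied SD: 1.785 / √(2/115.5) = 13.56. As a check, an SD of 13.5 gives 115 evaluable and 165 enrolled per arm, with 80.4% power.

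**Contrast.** Protocol 13.3 keeps the strata from overlapping ("If duplicate surveys are identified, the first will be retained, and the second will be excluded from the research"), so the variances add: SE = √2 × 1.785 = 2.524. The 95% half-width is 1.960 × 2.524 = 4.947. Power for a 5-unit difference is Φ(5/2.524 − 1.960) = 51%. The difference detectable with 80% power is 2.802 × 2.524 = 7.07 units.

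At SD 13.56:

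| Retention | Contrast SE | 95% half-width | Power for 5 units | Exactly one stratum significant if both effects are 5 |
|---|---|---|---|---|
| 70% | 2.52 | 4.95 | 51% | 32% |
| 85% | 2.29 | 4.49 | 59% | 23% |
| 100% | 2.11 | 4.14 | 66% | 15% |

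The last column is 2p(1 − p), where p is the power in one stratum; at 70% retention, 2 × 0.8 × 0.2 = 0.32.

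At 70% retention, over assumed SDs:

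| SD | Contrast SE | Power for 5 units | Exactly one significant |
|---|---|---|---|
| 8 | 1.49 | 92% | 0.5% |
| 10 | 1.86 | 77% | 6.4% |
| 12 | 2.23 | 61% | 20% |
| 15 | 2.79 | 43% | 41% |

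If the sizing ignored the baseline adjustment in SAP 7.2.1, an assumed baseline correlation of 0.5 multiplies the SE by √(1 − 0.25) = 0.866. At SD 13.56, power is then 63% at 70% retention and 78% at full retention.

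**Imputation and the population contrast.** Arm and population both define the SAP 7.3 cells, so this contrast should survive imputation. A simulation used 600 trials per setting, 165 per arm per stratum, residual SD 13.56, baseline correlation 0.5, outcomes missing completely at random, and 20 imputations. With a true arm × population difference of 5 it returned 5.12 and 5.09 (Monte Carlo SE 0.11) at 30% missing, for subgroup prevalences of 50% and 13%.

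**Imputation and the other subgroups.** When the donor cell omits the subgroup, imputed records carry no subgroup difference in effect. If missingness is unrelated to subgroup, a true difference D becomes D × (1 − missing fraction): 5 × 0.70 = 3.5 and 5 × 0.85 = 4.25. The same simulation gave, for a true difference of 5 (Monte Carlo SE in brackets):

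| Missing | Subgroup prevalence | SAP 7.3 imputed data | Observed cases |
|---|---|---|---|
| 30% | 50% | 3.29 (0.11) | 4.80 (0.15) |
| 30% | 13% | 3.54 (0.15) | 5.26 (0.22) |
| 15% | 50% | 4.21 (0.11) | 4.96 (0.13) |
| 15% | 13% | 4.13 (0.17) | 4.83 (0.20) |

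The 13% prevalence is 72/560, the Hispanic share of the Aim 2 ethnicity counts in Protocol Table 3.

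**The case against.** The sentence about differing magnitude can be read simply as the reason for fitting separate models. The next sentence sets the goal as evidence in healthcare workers, and the stratum models deliver it. The formal Aim 2 hypothesis does not mention heterogeneity. The difference and its CI can be derived from the two reported CIs, so no information is lost. All of this stands, and it is why the point is an improvement and not a defect.

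Three stronger readings are tempting, and the documents support none of them:

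- A reader might infer that heterogeneity will be judged by one stratum being significant and the other not. No passage plans this. The 32% figure shows how such a comparison would mislead; it does not describe a planned analysis.
- A reader might infer that the claim of being statistically powered, in Protocol 13.5 and SAP 5.4, is wrong. It refers to each stratum's own estimate, not to their difference.
- A reader might call the contrast simply underpowered. With no SD stated, power for 5 units could be as high as 92% or as low as 43% at 70% retention. What can be said is that the sample size was not set for it.

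On subgroups, SAP 7.2.3 leaves the data source open, so the shrinkage follows only if the general SAP 7.3 rule is applied. Protocol 13.4 promises to examine sensitivity to the imputation approach and variables, and SAP 5.3 allows additional data sets imputed by other techniques. These provisions soften the point but do not settle it, because none puts the subgroup into the donor cells.

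**Conclusion.** The gap is real but modest. The stratum analyses are valid and should stay primary. What is missing is a pre-specified estimate for a hypothesis the protocol states, with a warning about its precision. At 70% retention, equal stratum variances and the back-solved SD of 13.6, that estimate would carry a 95% CI of about ±4.9 units, nearly as wide as the 5-unit effect for which each stratum was sized. The √2 ratio to a stratum SE needs only equal stratum variances; the figures in units depend on an SD that the documents do not give.

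The subgroup point is distinct and conditional. On SAP 7.3 data as they stand, differences between subgroup effects shrink by roughly the missing fraction, if missingness is unrelated to subgroup.

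**What to change.** **Population contrast.** Keep SAP 7.2.1 as primary. Add to SAP 7.2 one secondary estimate for the primary outcome: effect in patients minus effect in providers/staff, with its 95% CI, pooled over the 20 imputed data sets. The same contrast is the arm × population term (patients coded 1) in one model with arm, population, baseline score, arm × population and baseline × population, using robust SEs. The SAP 7.3 cells need no change for this. State that:

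- the sample size was not set for the contrast;
- its SE is about √2 times a stratum SE if stratum variances are equal, with the figures above given as conditional on the assumed SD and retention;
- a non-significant contrast does not show equal effects;
- differing significance between strata will not be read as heterogeneity.

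**Subgroups.** State in SAP 7.2.3 that subgroup effects will not use the SAP 7.3 imputed data as they stand. Two alternatives are sound: observed 6-month outcomes with baseline adjustment, assuming missingness depends only on arm, subgroup and baseline score; or an imputation that includes the subgroup.

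**Cost.** A few sentences in the SAP and one extra contrast on data already collected. Sample size, stratum estimates and primary imputation do not change. The small downside is that observed-case subgroup estimates need not reconcile exactly with the imputed stratum estimate.

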13.5 Sub-Group Analyses

We plan to generate different effect estimates for (1) providers and staff, and (2) patients and are statistically powered to do so. We also plan to produce separate effect estimates for the following subgroups: adult vs adolescent patients, types of providers, low baseline C-SSRS score vs moderate to high baseline C-SSRS score, Hispanic vs non-Hispanic, female vs male, cisgender vs transgender or gender-nonconforming, heterosexual vs. homosexual or bisexual, and urban vs rural; however, this study has not been specifically powered to identify differing treatment effects in each of these subgroups.

14. Engaging Providers & People with Lived Experience with Suicide

The research team for this trial includes people with lived experience with suicide, research scientists, system-level medical directors and administrators, physicians, psychologists, and social workers at SLHS; community partners at Jannus, including the Hotline and Empower Idaho, and, the Idaho Federation of Families for Children's Mental Health (IFF); suicide prevention researchers as well as dissemination, biostatistics, and bioethics experts at the University of Washington.

Study staff will continue to engage and expand the scope for the existing *People with Lived Experience with Suicide (PLES) Advisory Board* to support this trial. Study staff will convene a formal PLES Advisory Board to include up to 15 people who experienced suicidality as adults or adolescents. The PLES Advisory Board will provide input related to specific questions (such as study branding, recruitment strategy, the informed consent process (including readability of consent forms), retention techniques, and the content, frequency, and timing of the messages included in Caring Contacts), and will assist with the dissemination strategy.

Study staff will continue to engage the SLHS Behavioral Health providers and a cross-functional group of stakeholders at SLHS for input on study design, conduct, and dissemination of study results.

Multiple staff and providers perspectives will be represented including system- and clinic-level providers including, for example, patient access specialists, social workers, psychiatrists and psychologists, ED physicians, pediatricians, and primary care physicians, advanced practice providers, and medical assistants and nurses. Process evaluation will be used to assess what providers and staff think about the specific messaging included in the Caring Contacts. Study staff will also engage an existing group of stakeholders within the health system who are dedicated to provider and employee well-being, to solicit input related to the MHAPPS Trial without burdening health system staff responding to COVID-19.

Study staff will continue to engage existing MHAPPS stakeholders at the state, regional, and community levels, including but not limited to public sector stakeholders, private foundations, and non-governmental organizations.

MHAPPS Trial Protocol

SLHS Applied Research

December 30, 2020

15. Risk / Benefit Analysis

15.1 Potential Risks

There are several potential risks to participation in this study. Loss of confidentiality due to the unintended release of sensitive information is one risk. This risk will be mitigated by storing all electronic data on password protected servers. Data will be shared among research partners through REDCap.

REDCap is a secure, HIPAA-compliant web-based research data management application, used for building and managing online surveys, and providing a secure electronic database. REDCap is owned and managed by the University of Washington's Institute of Translational Health Sciences (ITHS).

REDCap will be used as a central location for online study data storage and participant management. Use of REDCap will protect against unintended release of sensitive information.

Other potential risks include psychological distress from completing study questionnaires related to loneliness, anxiety, depression, suicidality, other mental distress, and quality of life. The frequency of contact in the follow-up intervention may also cause emotional distress. Research participants will be reminded at enrollment that they may quit the survey or skip any questions (Aim 1) or leave the study (Aim 2) at any point with no consequences to the care they receive at SLHS (patients) or their employment (providers/employees). Participants will be reminded of resources (including the Hotline and, if appropriate, behavioral healthcare services) that they can access as needed in the event of psychological distress. Participants will not be enrolled in Aim 2 of the study if they are in an acute crisis or if they are unable to provide informed consent to participate. Additionally, measures will be put in place to support any individuals who report high levels of suicide ideation using a modified version of the St. Luke's Health System Red Flag Workflow, which is the standard safety protocol for any individual who contacts the health system and reports suicidal ideation. In the modified version, all individuals endorsing acute suicide risk would be connected to the Idaho Suicide Prevention Hotline using a warm-handoff. Section 16.2.2 of this protocol details how study staff will assess and respond to acute crisis.

Study staff (including anyone involved in enrollment and informed consent or delivery of the follow-up intervention or outcome measurements, and/or having access to patient-level data) will be trained on the protection of human subjects and HIPAA, with a focus on topics relevant to confidentiality. SLHS staff will assist participants in completing Aim 2 informed consent, and REDCap survey links will be sent out via text, email, or MyChart. Study staff at SLHS, University of Washington and the Hotline will have access to protected health information (PHI).

The study is designed to be low burden in terms of participants' time. The initial survey (Aim 1) will consist of up to 50 multiple choice questions. Those participants who enroll in the comparative effectiveness trial (Aim 2) will complete a baseline survey (up to 50 questions), receive 11 caring text messages over a 6-month period, and depending on intervention arm, may also receive an introductory

phone call. Aim 2 study participants will complete an outcomes assessment survey online, which will consist of up to 50 questions. Participants will be reimbursed for their time.

Participants will be under no duress or pressure to participate in or complete this study.

- *Patient Participants.* Participating in this study will not impact the care they receive, and this will be clearly communicated to participants as part of the informed consent process.
- *Provider/Staff Participants.* Participating in this study will not impact their employment, and information received in this study will not be shared outside of the study staff. This will be clearly communicated to participants as part of the informed consent process.

